6. STRATA AND COVARIATES

6.1. Stratification variables

Randomisation is stratified by the following:

- Disease severity (baseline SASSAD ≥10 to ≤ 20, or SASSAD score >20)
- Recruiting centre

6.2. Other covariates

In addition to the stratification variables, other covariates to be considered in a predictors of response model are:

- Age (continuous)
- Previous treatment history (see section 8.3)
- Water hardness at baseline (WHO classification, continuous).
- Sex
- Ethnicity
- Filaggrin status
- Income
- Time away from home (based on a cut off of >21 days).

In addition, the following baseline characteristics will be summarised:

Washing powder

- Fabric softener
- Bathing/showering frequency
- Swimming frequency
- Home ownership
- Allergy

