5.5 Starting and stopping treatment

Units will be installed in the participants' homes as soon as possible after being randomized to treatment (ideally within 10 working days).

If participants choose to withdraw from the study, any units that have been installed will be removed as soon as is practicably possible. Participants will be asked to complete an end of study questionnaire at this time and diaries will be collected.

If participants are away from the main residence for any reason, this information will be recorded in their treatment diaries. Absence from the home will be included in a predictors of response model and will be used as a measure of treatment adherence for the (secondary) per protocol analysis.

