6.3 Further exploratory analyses

In addition to the main outcomes listed above, further exploratory analyses are planned as follows

• Difference in mean change in disease severity (SASSAD) at 4 weeks compared to

baseline. This outcome is included in order to capture speed of onset of benefit.

- Further within person analyses will be conducted comparing outcomes collected during the final 4-week period (12 to 16 weeks), with those collected during the initial 4 weeks of the study (0 to 4 weeks). Data collected for the active treatment group will provide an indication of the likely carry-over effect of this intervention, which will be useful in planning the design of future trials in this area. Data collected for the delayed treatment group will inform the analysis regarding speed of onset of improvement.
- Predictors of response model including baseline factors such as filaggrin status (see later section), baseline eczema severity, water hardness, swimming activity and time away from the home).

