7.2 Exclusion criteria

- Children who plan to be away from home for >21 days in total during the 16-week study period. This has been deemed necessary in order to ensure adequate exposure to the intervention. We will also aim to ensure children do not have a planned holiday in the 4 weeks prior to their 12 week assessment visit.
- Children who have taken systemic medication (e.g. Cyclosporin A, methotrexate) or UV light for their eczema within the last 3 months because of their long lasting effects.
- Children who have taken oral steroids within the last 4 weeks, or who, as a result of seeing a healthcare professional, have started a new treatment regimen for eczema within the last 4 weeks.
- Families who already have a water treatment device installed, including ion-exchange softeners, polyphosphate dosing units or physical conditioners.

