9.1.2. Treatment diaries

Diaries will be used to capture:

- i. the number of days when active topical treatment (topical corticosteroids, tacrolimus or pimecolimus) is applied
- ii. whether or not treatment has needed to be "stepped up" if so, in what way and for how many days ("stepping up" treatment will be defined in advance by the parents in consultation with the research nurse)
- iii. daily global assessment of disease activity by child and parents
- iv. nights away from home

³ Target lesion nominated by research nurse in discussion with the child/parents.

- v. health service resource use
- vi. personal costs associated with the eczema
- vii. whether or not the accelerometers have been worn (weeks 1 and 12).

Items i) and ii) above will be used to calculate the number of totally controlled weeks (TCW) and well controlled weeks (WCW) during the study. Diaries will also be used to remind participants to check the salt levels in the machine and to return a sample of the water for testing in the laboratory every week.

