9.2. Compliance

Absence from the home will be used as the measure of compliance (recorded on the symptom diary).

A log of all protocol deviations will be kept by the Trial Manager which will be reviewed by the protocol violations committee at the end of the trial in order to assign the events as major or minor protocol deviations. Participants with major deviations will be excluded from the per protocol analysis.

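### The response model splits time away from home at the entry-exclusion threshold of 21 days and gives no time window, so the upper group is likely to be sparse and all variation below 21 days is lost

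*Combined protocol and SAP*

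**What the plan says.** SAP 6.2 gives the covariates for the predictors-of-response model. Age and baseline water hardness are marked continuous. Absence is entered as "Time away from home (based on a cut off of >21 days", with no period over which the days are counted. SAP 10.3 fits two logistic regressions, with response defined as a 20% or a 50% fall in SASSAD. SAP 3.3 makes these analyses conditional on a beneficial effect being found.

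Protocol 7.2 excludes "Children who plan to be away from home for >21 days in total during the 16-week study period" and gives the reason: "This has been deemed necessary in order to ensure adequate exposure to the intervention". It adds a softer aim: "We will also aim to ensure children do not have a planned holiday in the 4 weeks prior to their 12 week assessment visit".

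The protocol intends absence to be studied. Section 5.5 says "Absence from the home will be included in a predictors of response model" and also uses absence as an adherence measure for the per protocol analysis. Section 6.3 names "swimming activity and time away from the home" among the predictors. SAP 9.2 says "Absence from the home will be used as the measure of compliance (recorded on the symptom diary". The raw data are a count: protocol 9.1.2 has the diaries record "nights away from home".

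**The concern.** The model splits children at the value that the entry rule selects against. To fall above the cut, an enrolled child must have been away for longer than the plan accepted at entry. Everyone from no absence to three weeks of absence goes into the reference level, and that is where most enrolled children should lie. A sparse binary term carries little information, so a null result for absence would say little about whether absence affects response.

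The window is a separate gap. Response is judged at week 12, whereas the entry limit runs over 16 weeks. If the covariate is also counted over 16 weeks, nights away after the outcome visit help to predict that outcome.

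At stake is the usefulness of one exploratory predictor that the protocol twice says it will examine. The treatment comparison is not at stake.

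**Working it through.** **Evaluable number.** SAP section 4 gives a difference of 20% of a baseline mean of 20, which is 4 points, with SD of change 10, 90% power, 5% significance (taken as two-sided) and 15% attrition.

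- Per arm: 2 × [10 × (1.960 + 1.282) / 4]² = 131.4, rounded up to 132, so 264 in total.
- Inflated for attrition: 264 / 0.85 = 310.6, rounded up to 311, against 310 stated. The plan's figure reproduces.
- 310 × 0.85 = 263.5, so about 264 evaluable children is the working number.

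**Share above the cut.** The documents give no expected or observed figure, so it is varied. Let k be the number above 21 days and 264 − k the rest. Assume 20% responders above the cut and 40% below (neither rate is in the documents). With p̄ the pooled rate:

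- SE₀ = √[p̄(1 − p̄)(1/k + 1/(264 − k))]
- SE₁ = √[0.2 × 0.8/k + 0.4 × 0.6/(264 − k)]
- power = Φ[(0.20 − 1.96 × SE₀) / SE₁]

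Example at 5%: k = 13.2, p̄ = 0.39, SE₀ = 0.1377, SE₁ = 0.1144, so power = Φ(−0.61) = 27%.

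| Share above 21 days | Children (of 264) | Power, 20% v 40% responders | Power, 4 SASSAD points (SD 10) |
|---|---|---|---|
| 1% | 3 | 5.6% | 9.5% |
| 2% | 5 | 10.5% | 15% |
| 5% | 13 | 27% | 29% |
| 10% | 26 | 52% | 50% |
| 20% | 53 | 80% | 74% |
| 50% (even split) | 132 | 95% | 90% |

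The last column is for reference, using the SAP's own effect size: power = Φ[4 / (10√(1/k + 1/(264 − k))) − 1.96]. These are unadjusted normal approximations, rough in the top rows. A model with the other covariates would generally do no better.

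**Arm.** Group B has no softener before week 12, so absence means lost exposure only in Group A. The same formula with 132 children gives 13%, 26% and 48% power at 5%, 10% and 20% above the cut.

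**Non-estimability.** If 40% respond overall (assumed), the chance that all k children above the cut share one outcome is 0.4^k + 0.6^k. This is 28% for k = 3, 9% for k = 5 and 0.1% for k = 13.

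**Window.** 21 days is 21/112 = 18.75% of 16 weeks and 21/84 = 25% of 12 weeks, so the same cut means different things under the two readings. Protocol Table 1 has Diaries 1 and 2 collected by the week-12 visit, so nights away up to the outcome can be separated from later nights. That visit may fall anywhere from 12 to 14 weeks, so a proportion of diary nights is more comparable between children than a fixed day count.

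**The case against.** Protocol 7.2 bars planned absence, whereas the covariate would reflect actual absence. Plans change, and no document says how many children would exceed 21 days. This stands. A reader might infer that the upper group is almost empty and that the model cannot show an effect; the documents support only that the group is likely to be sparse. If 20% exceeded the cut, power in the pooled comparison would be about 80%. A reader might also expect the term to separate perfectly; the figures above make that possible with three to five children and very unlikely with thirteen.

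It is also tempting to argue that counting to week 12 demands a higher rate of absence than the entry rule bars. That fails: the entry limit is a total, and all of it may fall before week 12. A child who planned 21 days away in the first eight weeks needs only one more night to cross the cut.

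The cut may have a rationale. Over 12 weeks, more than 21 days away corresponds to the Group A per protocol criterion of under 75% exposure in SAP section 5, if the unit works and is in place throughout. But the SAP does not give this reason for the covariate, and it would not justify discarding the variation from 0 to 21 days.

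Absence is handled in the per protocol criteria too, with different cut-offs. Those rules remove children from an analysis; they do not estimate how response varies with absence.

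Finally, the model is tertiary, conditional on benefit, described as exploratory in protocol 6.3, and its covariates are only to be considered. All of that stands and limits the importance of the point.

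**Conclusion.** The point holds as a low-severity improvement. Two parts rest on the text alone: the covariate is cut at the number used for the entry exclusion, which discards all variation from 0 to 21 days, and no counting window is stated. The loss of power depends on the assumed share above the cut and the assumed 20% and 40% response rates: about 6% to 27% power if 1% to 5% of 264 children exceed the cut, 52% at 10% and 80% at 20%. The documents do not establish which share applies. Use of post-outcome absence arises only if the days are counted over 16 weeks. The primary analysis and its inference are unaffected.

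**What to change.** In SAP 6.2, replace the 21-day cut with nights away from the diary as a continuous variable, counted up to the week-12 SASSAD visit and divided by the number of diary nights in that period. Fit it either with an arm interaction, counting from baseline in both groups so that the term has one meaning, or within Group A alone, counting from installation. Report the number of children above 21 days by group as a description of how actual absence compared with the entry limit.

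The cost is a line or two of SAP wording. The diary data are already collected. The downside is that linearity of the term has to be checked. Restricting to Group A also halves the sample, so even the better-coded term should be reported with its confidence interval and not judged by significance alone.

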7. PLANNED SUBGROUP ANALYSES

A sub-group analysis will be conducted based on the presence or absence of mutations on the filaggrin gene (collected using spit samples). Mutations on the filaggrin gene have been associated with dry skin and may therefore be a useful predictor of treatment success. The planned subgroup analysis will only be performed on the primary outcome of change in SASSAD score. The p-value for the interaction will be reported.

Assuming that the presence of at least one mutation in the gene encoding filaggrin results in improved treatment response, a total of 90 children with at least one such mutation would be sufficient to detect a 30% difference between the treatment groups in the primary outcome, with 80% power, 5% significance (2 sided) and a standard deviation of 10. Allowing for a 20% drop out means that 120 children would need to carry the gene mutation. For 90% power this figure would be 145.

8. DATA HANDLING

8.1. Missing data

The primary outcome is collected by nurses at study visits so missing items are not expected. Other missing data items such as age, sex, etc. will be queried so that there are no missing data for these variables.

Missing baseline water hardness score will be replaced with published water hardness data for that postcode.

For each endpoint the number with a missing outcome for each treatment group will be reported with reasons given where available.

If less than 5% of data are missing for the primary endpoint only participants with complete data will be included in the full ITT primary analysis. An additional sensitivity analysis will be conducted replacing missing data with the maximum value at baseline and week 4 (where this exists). If more than 5% of data are missing for the primary endpoint then more complex multiple imputation techniques will be used to handle the missing values. Secondary endpoint analyses will be analysed using a complete case analysis as these are only considered supportive of the primary endpoint analysis.

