6.2 Secondary outcomes

1. Difference between the groups in the proportion of time spent moving during the night². Movement will be captured for periods of one week at week 1 and week 12, and will be measured using accelerometers (ActiwatchTM). These units are worn by the child in the same way as a wrist watch

² This outcome has been included as an objective surrogate for sleep loss and itchiness (two of the defining features of eczema). Previous research has suggested that this is a suitable objective tool for assessing itch ^{6,7} and further pilot work is currently underway to assess its suitability for use within this trial (results available Dec 2006)

This outcome has been included as an objective surrogate for sleep loss and itchiness (two of the defining features of eczema). Previous research has suggested that this is a suitable objective tool for assessing itch ^{6,7} and further pilot work is currently underway to assess its suitability for use within this trial (results available in 2007).

- 2. Difference in proportion of children who report either good or excellent improvement in eczema severity at 12 weeks (using a 5-point Likert scale).
- 3. Difference in the amount of topical corticosteroid / calcineurin inhibitors used during the 12 week study period.
- 4. Difference in Patient Oriented Eczema Measure (POEM ⁸) collected at baseline, weeks 4, 12 and 16. This scale is a well validated tool that has been developed to capture symptoms of importance to patients (rather than objective signs that are used in traditional severity scales, such as SASSAD).
- 5. Difference in the number of totally controlled weeks (TCW) and well controlled weeks (WCW) based on the number of days with eczema symptoms and the number of days that topical treatment is applied. This outcome is based on a recent systematic review conducted by the applicants looking at ways of assessing long-term control for chronic conditions such as atopic eczema, asthma and rheumatoid arthritis ⁹. The terms TCW and WCW have been adopted for use by researchers in the field of asthma and appear to be a useful and intuitive means of capturing disease activity over time.
- 6. Difference in the mean change in the Dermatitis Family Impact (DFI) questionnaire at 12 weeks ¹⁰. This scale was chosen as an appropriate quality of life scale for the study for two reasons:

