4. SAMPLE SIZE

Sample size estimates are based on other published data relating to the use of SASSAD in patients recruited in secondary care. Based on a minimum clinically relevant difference of 20% in the change in SASSAD score between the 2 groups, and assuming a mean baseline SASSAD score of 20 with a standard deviation in change scores of 10, a sample size of 310 children will provide 90% power, with a significance level of 5% allowing for an attrition rate of 15%.

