10.2. Secondary Efficacy Analyses

- 1) The difference between baseline and week 12 of the proportion of time spent moving during the night will be compared across intervention groups using a t-test. The average of the first three nights of evaluable data at week 0, and the last three nights at week 12 will be used.
- 2) The proportion of children who report a reasonable (≤20%), good (>20% and ≤50%) or excellent (>50%) improvement in SASSAD score at 12 weeks, will be compared using a chi-squared test.
- 3) Amount of topical corticosteroid / calcineurin inhibitors used during the 12 week study period. This will be captured by weighing the medication at each visit. This will then be summarised by the nurses at week 12, including a measure of the degree of accuracy of any estimates. These will be spilt into two groups, low strength consisting of mild and moderate topical steroids, and high strength consisting of potent and very potent topical steroids and mild and moderate calcineurin inhibitors. The difference in the amount (in grams) of each of the two groups will be assessed using t-tests.
- 4) The difference in the change from baseline to week 4 and baseline to week 12 Patient Oriented Eczema Measure (POEM) scores will be compared using t-tests.
- 5) Difference in the number of well controlled weeks (WCW) as defined in section 8.3, will be analysed using a t-test. The number of totally controlled weeks (which are a subset of the WCW), will also be summarised.
- 6) Difference in the mean change from baseline in the Dermatitis Family Impact (DFI) questionnaire at 12 weeks, will be analysed using a t-test.

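### Above 5% missing SASSAD, the SAP imputes the primary outcome but drops the same children from week-12 POEM and DFI; supportive status does not make that dropout harmless

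*Combined protocol and SAP*

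**What the plan says.** SAP 8.1 has three rules.

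- **Primary endpoint, little missing:** "If less than 5% of data are missing for the primary endpoint only participants with complete data will be included". A sensitivity analysis then fills each gap with the larger of the baseline and week-4 SASSAD.
- **Primary endpoint, more missing:** "If more than 5% of data are missing for the primary endpoint then more complex multiple imputation techniques will be used".
- **All secondary endpoints, whatever is missing:** "Secondary endpoint analyses will be analysed using a complete case analysis as these are only considered supportive of the primary endpoint analysis".

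It also promises a description of the losses: "For each endpoint the number with a missing outcome for each treatment group will be reported with reasons given where available". No missing-data sensitivity analysis is attached to any secondary endpoint.

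SAP 4 sets the sample size "with a significance level of 5% allowing for an attrition rate of 15" per cent. Protocol 5.2 expects less than that, takes 15% as the cautious figure, and reports that the pilot lost no child by its final visit.

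Protocol 6.2 item 4 has POEM "collected at baseline, weeks 4, 12 and 16". SAP 10.2 item 4 compares "The difference in the change from baseline to week 4 and baseline to week 12 Patient Oriented Eczema Measure (POEM) scores" by t-tests. Protocol Table 1 puts SASSAD, POEM and the utility measures (DFI and EQ-5D) at the same 12-week nurse visit. At week 4 it lists SASSAD and POEM but no utility measures.

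**The concern.** The reason given for complete-case analysis is the standing of the endpoints. That can justify leaving multiplicity unadjusted, as SAP 5 does. It does not bear on whether the children who leave resemble those who stay. For the primary endpoint, the same section accepts that more than 5% missing needs more than a complete-case analysis.

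A child who misses the 12-week visit loses SASSAD, POEM and DFI together. Above the 5% trigger that one missed visit is handled in two ways: SASSAD is imputed, and POEM and DFI are dropped. Week-4 POEM has its own test, but week-4 data do not inform the week-12 POEM or DFI contrast.

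Families are not blinded (protocol 8.3). Group A lives with the unit and its salt; Group B is waiting for one. Reasons for leaving may therefore differ by arm. If they do, the parent-reported results can shift for reasons unrelated to the softener. A gap between them and SASSAD could then be misread as response bias or as symptom benefit, when part of it comes from different missing-data handling.

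**Working it through.** **1. The plan's own sample size.** Inputs from SAP 4: difference 20% of 20 = 4 points, SD 10, 90% power, 5% significance, 15% attrition. Two-sided testing is assumed; SAP 7 states it only for the subgroup calculation.

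n per arm = 2 × (1.96 + 1.2816)² × 10² / 4² = 131.3, so 132 per arm and 264 in total. Inflated: 264 / 0.85 = 310.6, or 309.0 without rounding first. The stated 310 reproduces.

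**2. Which rule applies at the planned loss.**

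- 5% trigger: 0.05 × 310 = 15.5 children.
- Planned loss: 0.15 × 310 = 46.5 children, three times the trigger.
- Children with week-12 POEM and DFI: 0.85 × 310 = 263.5, about 264.

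On the plan's own allowance, the imputation rule governs SASSAD and the complete-case rule governs POEM and DFI.

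**3. What complete-case analysis can do.** Let m be the fraction missing in an arm, and g the mean of missing minus observed children in SD units. Then

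bias (A − B) = mB × gB − mA × gA.

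With equal m and equal g the bias is zero. If only Group A's loss is informative and m = 0.15, its size is 0.15 × |gA|; for example, 0.15 × 0.5 = 0.075 SD.

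**4. Simulation for a POEM-type change score.** Neither document gives the inputs, so they are assumptions: 155 per arm, no true effect, 15% loss per arm, random loss in Group B. In Group A the odds of loss rise by the stated ratio per SD less improvement at week 4.

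| Week-4 to week-12 correlation | Odds ratio | Complete-case bias (SD, favouring the softener) | Type I error |
|---|---|---|---|
| 0.3 | 1.5 | 0.020 | 4.9% |
| 0.3 | 2 | 0.033 | 6.1% |
| 0.3 | 3 | 0.045 | 6.7% |
| 0.6 | 1.5 | 0.035 | 6.0% |
| 0.6 | 2 | 0.060 | 7.4% |
| 0.6 | 3 | 0.083 | 10.4% |

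Repeat runs at correlation 0.6 agreed within simulation error (0.030 to 0.088 SD, error up to 10.7%). By step 3, a bias of 0.083 SD means that the missing Group A children did 0.083 / 0.15 = 0.55 SD worse than those observed; 0.020 SD means 0.13 SD worse.

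Sensitivity to the assumptions:

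- Same mechanism in both arms: bias 0.000 to 0.002 SD, error 4.4% to 5.3%.
- 8% loss: bias 0.019 to 0.050 SD, error 5.2% to 6.7%.
- Correlation 0.4 to 0.8: bias 0.03 to 0.11 SD, error 5.6% to 14.9%.
- Unequal loss (10% and 20%) with differing mechanisms: bias 0.07 to 0.16 SD, error 9% to 25%. The documents give no ground for expecting that split.

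**5. What week-4 data recover.** Regressing week-12 change on week-4 change within arm leaves a bias of 0.003 SD or less when dropout depends only on week-4 response. When Group A's dropout depends on week-12 status itself, it leaves 0.042, 0.064 and 0.093 SD for the three odds ratios, about two-thirds of the complete-case bias.

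**6. Reach of these figures.** They apply to POEM. Table 1 has no week-4 DFI, and controlled weeks have no week-12 change score, so for those only the formula in step 3 carries over.

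**The case against.** The best defence has four parts.

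- **The mismatch may not arise.** Below 5% missing, SASSAD is also analysed on complete cases and the sets largely coincide. The pilot lost no one. This stands: a reader might infer that SASSAD is always imputed for a missed visit, but SAP 8.1 makes that conditional.
- **Week-4 data are used.** A child with week-4 POEM only still counts in the week-4 POEM test, and week-4 SASSAD enters the replacement sensitivity analysis. This also stands. It would be wrong to infer that week-4 data are ignored for children who miss week 12; the gap is confined to the week-12 secondary contrasts.
- **Other protections exist.** The primary outcome is assessed blind, photographs are graded independently, unblinded assessments are excluded in a sensitivity analysis, and losses are reported by arm. A reader might take the comparison of SASSAD with parent reports to be the trial's main safeguard; no section says so. Reporting counts would make unequal loss visible but would not correct an estimate.
- **The bias is assumed, and the remedy is imperfect.** The table lets only Group A's dropout be informative. With a shared mechanism the bias vanishes, and step 5 shows that the remedy fails in part when dropout follows unseen week-12 status. This limits the size of the claim. It does not supply a reason for the complete-case rule.

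Controlled weeks do not belong to the argument about a shared missed visit. They come from daily diaries, which are collected on withdrawal (protocol 5.5, SAP 9.3). What the SAP lacks for them is a rule for a partly filled 12-week diary.

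Nor does imputation add observed outcomes: SASSAD on 310 would still contain about 264 measured values. SAP 5 limits the ITT population to children with evaluable data, which fits poorly with imputing SASSAD.

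**Conclusion.** The point holds as a conditional risk. If more than 5% of SASSAD is missing, the plan handles one missed visit in two ways, and supportive status does not justify the difference. At the 15% allowance, week-12 POEM and DFI rest on about 264 children while SASSAD is imputed for the other 46 or so.

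For a POEM-type score the bias is about 0.02 to 0.09 SD and the type I error about 5% to 11%. This assumes 15% loss, a correlation of 0.3 to 0.6, and dropout related to week-4 response in Group A only (odds ratio 1.5 to 3 per SD). The upper figure is somewhat under a quarter of the 0.4 SD (4/10) for which the trial is powered on SASSAD: 0.09 / 0.4 = 0.23. With random dropout, or the same mechanism in both arms, there is no bias.

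A reader might go further and infer that the parent-reported results will be biased towards the softener. The documents do not support that: they say nothing about how dropout will relate to response, and other mechanisms would reverse the sign. The primary inference and the stated power are untouched.

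**What to change.** Replace the sentence on secondary endpoints in SAP 8.1 as follows.

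- **POEM:** one mixed model on weeks 4 and 12, with arm by visit and baseline POEM, reporting both the week-4 and week-12 contrasts. This replaces the two t-tests in SAP 10.2 item 4.
- **DFI:** when SASSAD is multiply imputed, include week-12 DFI in the same imputation model, with baseline DFI and week-4 SASSAD and POEM as predictors.
- **Controlled weeks:** use the diary weeks observed before withdrawal rather than excluding the child, and define how a partly filled diary counts.
- **Sensitivity:** keep the complete-case analyses. State that the main method assumes missing at random and does not remove bias from dropout driven by unobserved week-12 status.
- **Population:** reconcile the ITT definition in SAP 5 with the imputation rule in SAP 8.1.

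The cost is SAP wording and a little programming. The visits and scores are already collected, and imputation is already foreseen for SASSAD. The drawback is slightly more complex secondary models. Protocol 8.3 has the analysis plan finalised before the coded allocation is revealed, so the change should be made before then.
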